Appendix E. Guidelines for hemoglobin (Hb) decrease ≥ 1.5 g/dL

[figure not shown]

Suspicion of hemolytic anemia is recorded as AE only if:

- Symptomatic and/or
- Requiring either corrective treatment or consultation, and/or
- Leading to IMP discontinuation or modification of dosing, and/or
- Fulfilling a seriousness criterion

* If a second hemoglobin measurement demonstrating a further decrease of ≥ 1 g/dL from the last available value is observed, even if the previous work-up was negative, the same investigations can be repeated and a hematology consultation can be requested at the discretion of the Investigator or at the Sponsor's request.

## LIST OF ABBREVIATIONS AND DEFINITION OF TERMS

Ab:	antibody
ADA:	anti-drug antibody
AE:	adverse event
AESI:	adverse event of special interest
ALP:	alkaline phosphatase
ALT:	alanine aminotrasferase
ANCOVA:	analysis of covariance
ANOVA:	analysis of variance
Apo:	apolipoprotein
AST:	aspartate aminotransferase
ATC:	anatomic therapeutic category
CEC:	clinical events classification
CHD:	coronary heart disease
CI:	confidence interval
CKD:	chronic kidney disease
CV:	cardiovascular
CVD:	cardiovascular disease
ECG:	electrocardiogram
e-CRF:	electronic case record form
eDISH:	evaluation of drug-induced serious hepatotoxicity
EZE:	ezetimibe
GGT:	glutamyl transferase
HbA1c:	glycated hemoglobin A1c
HCV:	hepatitis C virus
HDL-C:	high density lipoprotein cholesterol
HLGT:	high level group term
HLT:	high level term
IMP:	investigational medicinal product
ITT:	intent to treat, intent-to-treat
IVRS:	interactive voice response system
IWRS:	interactive web response system
LDH:	lactate dehydrogenase
LDL-C:	low density lipoprotein cholesterol
LLOQ:	lower limit of quantification
LLT:	lowest level term
LMT:	lipid modifying therapy
LS:	least square
MAR:	missing at random
MCMC:	Markov Chain Monte Carlo
MedDRA:	medical dictionary for regulatory activities
MI:	myocardial infarction

MMRM:	mixed effect model with repeated measures
NMAR:	not missing at random
PAD:	peripheral arterial disease, peripheral arterial disease
PCSA:	potentially clinical significant abnormality
PK:	pharmacokinetics
PT:	preferred term
Q1:	first quartile
Q2W:	every 2 weeks
Q3:	third quartile
QQ:	quantile quantile
RDW:	red blood cell distribution width
SAEs:	serious adverse events
SD:	standard deviation
SOC:	system organ class
TC:	total cholesterol
TG:	triglycerides
ULN:	upper limit of normal range
ULOQ:	upper limit of quantification
WHO-DD:	World Health Organization-Drug Dictionary

## 1 OVERVIEW AND INVESTIGATIONAL PLAN

### 1.1 STUDY DESIGN AND RANDOMIZATION

This is a randomized, double-blind, parallel-group, double dummy, ezetimibe-controlled, unbalanced (2:1, alirocumab: ezetimibe), multi-center, multi-national study conducted in China, India and Thailand.

After a screening phase of up to 3 weeks, patients were centrally randomized via interactive voice response system (IVRS)/interactive web response system (IWRS) to 1 of the 2 treatment groups and treated in a double-blind manner for approximately 24 weeks.

Randomization was stratified according to:

- Prior history of myocardial infarction (MI) or ischemic stroke (Yes versus No);
- High-intensity statin treatment (Yes versus No; Yes defined as atorvastatin 40 to 80 mg daily or rosuvastatin 20 to 40 mg daily, No for simvastatin whatever the dose, atorvastatin below 40 mg daily or rosuvastatin below 20 mg daily);
- Country (China, India or Thailand).

Starting dose of alirocumab was 75 mg every 2 weeks (Q2W). A dose up-titration at Week 12 to 150 mg Q2W, depending on Week 8 low-density lipoprotein cholesterol (LDL-C) levels, may occur for patients randomized to alirocumab group. Patients will be followed for 8 weeks after the last visit of the double-blind treatment period.

Approximately 600 patients (400 in alirocumab and 200 in ezetimibe groups) were to be randomized from approximately 69 sites.

### 1.2 OBJECTIVES

#### 1.2.1 Primary objectives

The primary objective of this study is to demonstrate the reduction of low-density lipoprotein cholesterol (LDL-C) by alirocumab as add-on therapy to stable maximally tolerated daily statin therapy in comparison with ezetimibe (EZE) 10 mg daily after 24 weeks of treatment in Asia in patients with hypercholesterolemia at high cardiovascular (CV) risk.

#### 1.2.2 Secondary objectives

The secondary objectives are:

- To evaluate the effect of alirocumab 75 mg in comparison with ezetimibe 10 mg on LDL-C after 12 weeks of treatment.

- To evaluate the effect of alirocumab on other lipid parameters: eg, Apolipoprotein B (Apo B), non-high-density lipoprotein cholesterol (non-HDL-C), total cholesterol (TC), lipoprotein a (Lp[a]), high-density lipoprotein cholesterol (HDL-C), triglycerides (TG), and Apo A-1 levels).
- To evaluate the safety and tolerability of alirocumab.
- To evaluate the development of anti-alirocumab antibodies.
- To evaluate the pharmacokinetics (PK) of alirocumab.

### 1.3 DETERMINATION OF SAMPLE SIZE

[figure not shown]
A total sample size of 96 patients (64 in alirocumab and 32 in ezetimibe arms) will have 95% power to detect a difference in mean percent change in LDL-C of 20% with a 0.05 two-sided significance level and assuming a common standard deviation (SD) of 25% and all these patients having an evaluable primary endpoint.

Nevertheless, to meet registration requirement and provide safety documentation in participating countries the final total sample size will be 600 with a randomization ratio 2:1 (alirocumab: 400, ezetimibe: 0).

### 1.4 STUDY PLAN

The following figure presents the graphical study design:

**Figure 1 - Graphical study design**

\* Every effort should be made to ensure that the screening window is as short as possible and ideally within two weeks.

## **1.5 MODIFICATIONS TO THE STATISTICAL SECTION OF THE PROTOCOL**

There are no major changes to the protocol statistical section.

The first patient was screened on 27 July 2016(screen-failed). The first patient was randomized on 11 August 2016. There are no planned interim analyses.

## **1.6 STATISTICAL MODIFICATIONS MADE IN THE STATISTICAL ANALYSIS PLAN**

Not applicable.

## 2 STATISTICAL AND ANALYTICAL PROCEDURES

### 2.1 ANALYSIS ENDPOINTS

#### 2.1.1 Demographic and baseline characteristics

The baseline value is defined as the last available value obtained up to the date and time of the first double-blind investigational medicinal product (IMP) administration. The first double-blind IMP administration is defined as the earliest administration between the first double-blind injection date and the first capsule intake. For patients randomized and not treated, the baseline value is defined as the last available value obtained up to the date and time of randomization.

All baseline safety and efficacy parameters (apart from those listed below) are presented along with summary statistics in the safety and efficacy sections ([Section 2.4.4](#) and [Section 2.4.5](#)).

#### *Demographic characteristics*

Demographic variables are gender (Male, Female), race (Asian, other), age in years (quantitative and qualitative variable: <45,  $\geq 45$  to <65,  $\geq 65$  to <75, and  $\geq 75$  years; and <65, and  $\geq 65$  years).

#### *Medical history*

Medical history of specific interest includes:

- Coronary heart disease (CHD)
- CHD risk equivalents
- Cardiovascular (CV) risk factors other than hypercholesterolemia (hypertension, type 2 diabetes, type 1 diabetes, family history of premature CHD). Smoking status will be summarized separately.
- Family history of type 2 diabetes
- Patient's allergies (described using all pre-printed terms collected in the medical allergic history electronic case report form [e-CRF] page).

The CHD, CHD risk equivalents, and CV risk factors will be based on items or combination of items pre-listed in the dedicated medical history e-CRF page (unless otherwise specified).

CHD and CHD risk equivalents will be detailed as follows:

#### CHD (regardless if it is ongoing or not)

- Acute myocardial infarction
- Silent myocardial infarction
- Unstable angina
- Coronary revascularization procedure

- Other clinically significant CHD diagnosed by invasive or non-invasive testing

#### CHD risk equivalents

- Peripheral arterial disease (as defined in [Section 2.5.1](#))
- Ischemic stroke
- Moderate chronic kidney disease (as defined in protocol)
- Known history of diabetes mellitus AND 2 or more additional risk factors among:
  - History of ankle-brachial index  $\leq 0.90$ ;
  - History of hypertension;
  - History of microalbuminuria or macroalbuminuria or dipstick urinalysis at screening (Week -3/Week -2) with  $>2+$  protein;
  - History of pre-proliferative or proliferative diabetic retinopathy or laser treatment for diabetic retinopathy;
  - Known family history of premature CHD.

In addition, patients' status as primary and secondary cardiovascular disease (CVD) prevention will be summarized. Secondary CVD prevention is defined as patients with any of the following history of CVD (other patients will be classified as primary CVD prevention):

- History of CHD (as defined above)
- History of ischemic stroke
- History of peripheral arterial disease (PAD) with severity criteria defined as one of the following events:
  - Intermittent claudication and ankle brachial index  $\leq 0.90$ ;
  - Peripheral revascularization procedure (angioplasty, stenting) for PAD;
  - Thrombolysis for PAD;
  - Peripheral revascularization surgery (arterial bypass) for PAD;
  - Critical limb ischemia.

All medical history information pre-listed or not in the e-CRF, will be coded using the version of Medical Dictionary for Regulatory Activities (MedDRA) currently in effect at Sanofi at the time of database lock.

#### ***Disease characteristics at baseline***

Specific disease history includes:

- Lipid modifying therapy history, as reported in the "History of Hyperlipoproteinemia" e-CRF page:
  - Type of lipid-modifying therapy ever taken (statin, fibrates, bile acid sequestrant, cholesterol absorption inhibitor, nicotinic acid and derivates, omega 3 fatty acids  $\geq 1000$  mg/day, other);

- Number of patients taking atorvastatin 40 to 80 mg, rosuvastatin 20 to 40 mg or simvastatin 40 mg daily at screening and, for those not taking one of these agents at one of the specified doses, reasons for being on a lower dose or for not taking a statin.
- Background lipid modifying therapy (LMT) at randomization, as reported in the dedicated prior and concomitant medications e-CRF pages:
  - Number of patients taking high-intensity statin treatment (atorvastatin 40 to 80 mg, rosuvastatin 20 to 40 mg daily);
  - Atorvastatin daily dose in mg (10, 20, 40, 80, other);
  - Rosuvastatin daily dose in mg (5, 10, 20, 40, other);
  - Simvastatin daily dose in mg (10, 20, 40, other);
  - Any LMT other than statins;
  - Any LMT other than nutraceuticals (by chemical class and drug name);
  - Nutraceuticals (omega 3 fatty acids (<1000 mg/day), phytosterols, psyllium/plantago, policosanol, other nutraceuticals).

Details (ie, statin names, doses) for patients who had received at least 2 statins the day of randomization will be listed.

### ***Other baseline characteristics***

Other baseline characteristics include body mass index (BMI) in kg/m^2 (quantitative and qualitative variables: <30, ≥30), smoking status, alcohol habits and randomization strata (as defined in [Section 1.1](#)) as per IVRS and e-CRF.

Statin treatment stratum as per e-CRF will be derived using the statin name and dose taken the day of the randomization. If a patient takes neither atorvastatin, rosuvastatin nor simvastatin the day of randomization, stratum will be equal to the low/moderate dose stratum defined as “simvastatin whatever the dose, atorvastatin below 40 mg daily or rosuvastatin below 20 mg daily”. In case of combination of statins, stratum will be allocated to the high dose stratum defined as “atorvastatin 40 to 80 mg daily or rosuvastatin 20 to 40 mg daily” if at least one of the statins taken is in this category. If a patient takes atorvastatin, rosuvastatin or simvastatin the day of randomization but the daily dose is missing from the e-CRF, the stratification applied at randomization (ie, IVRS strata) will be applied.

Glycated hemoglobin A1c (HbA1c) (quantitative and qualitative variable: <5.7%, ≥5.7% to <6.5%, ≥6.5%), and efficacy lipid parameters (quantitative variables for all efficacy parameters and the following qualitative variables) will be also summarized at baseline (definitions in [Section 2.1.3](#)):

- calculated LDL-C: <1.81, ≥1.81 to <2.59, ≥2.59 to <3.37, ≥3.37 to <4.14, ≥4.14 to <4.91, ≥4.91 mmol/L;
- HDL-C: <1.04, ≥1.04 mmol/L;
- Fasting TG: <1.7, ≥1.7 to <2.3, ≥2.3 mmol/L, category ≥1.7mmol/L (mixed dyslipidaemia) will be also displayed;
- Lp(a): <0.3, ≥0.3 to <0.5, ≥0.5 g/L, category ≥0.3g/L will be also displayed.

Any technical details related to computation, dates, and imputation for missing dates is described in [Section 2.5](#).

### **2.1.2 Prior or concomitant medications**

All medications taken within 12 weeks prior to screening and until the end of the study, including LMTs are to be reported in the case report form pages:

- Previous and concomitant statin drugs;
- Previous and concomitant lipid lowering drugs (other than statins);
- Previous and concomitant medications (other than statin, lipid lowering drugs).

All medications will be coded using the World Health Organization-Drug Dictionary (WHO-DD) using the version currently in effect at Sanofi at the time of database locks.

Prior medications are those the patient used within 3 months to screening visit and prior to first double-blinded investigational medicinal product (IMP) administration (capsule or injection, whichever comes first). Prior medications can be discontinued before first administration or can be ongoing during treatment phase.

Concomitant medications are any treatments received by the patient concomitantly to the IMPs, from first double-blind IMP (capsule or injection, whichever comes first) to the last IMP injection +70 days. A given medication can be classified both as a prior medication and as a concomitant medication. Concomitant medications do not include medications started during the post-treatment period (as defined in the observation period in [Section 2.1.4](#)).

Post-treatment medications are those the patient took in the period starting from 71 days after the last IMP injection and ending when the patient terminates the study.

Any technical details related to computation, dates, imputation for missing dates are described in [Section 2.5](#).

### **2.1.3 Efficacy endpoints**

Efficacy parameters include lipid parameters (ie, TC, calculated LDL-C, measured LDL-C, HDL-C, fasting TG, non-HDL-C, Apo B, Apo A-1, Apo B/Apo A-1 ratio, Lp[a], TC/HDL-C ratio). All these parameters are measured or calculated by a Central Laboratory, for both scheduled and unscheduled time points. Calculated LDL-C is obtained using the Friedewald formula. Non-HDL-C is calculated by subtracting HDL-C from the TC. Measured LDL-C is obtained via beta quantification method. All measured LDL-C values provided by the Central Laboratory including those done in case of TG values exceeding 400mg/dL (4.52mmol/L) will not be used for the analysis of calculated LDL-C endpoints.

Unless other specified, all lipid values (scheduled or unscheduled, fasting or not fasting) may be used to provide a value for the primary and secondary efficacy endpoints. All measurements scheduled or unscheduled, fasting or not fasting, will be assigned to analysis windows defined in [Section 2.5.4, Table 2](#) in order to provide an assessment for Week 4 to Week 24 time points. For

TG, only fasting measurements will be used. Measurements with missing fasting status will be excluded from the analyses.

For all time points post-baseline, the value used for the analyses at a given time point (eg, at Week 24) is the value obtained within the corresponding analysis window. The baseline value is the last available measurement obtained up to the date and time of the first double-blind IMP administration (capsule or injection, whichever comes first). For patients randomized and not treated, the baseline value is defined as the last available value obtained up to the date and time of randomization.

### **2.1.3.1 Primary efficacy endpoint(s)**

The primary efficacy endpoint is the percent change in calculated LDL-C from baseline to Week 24 in the ITT population, using all LDL-C values regardless of adherence to treatment (ITT estimand). Primary endpoint is defined as:  $100 \times (\text{calculated LDL-C value at Week 24} - \text{calculated LDL-C value at baseline}) / \text{calculated LDL-C value at baseline}$ .

### **2.1.3.2 Secondary efficacy endpoint(s)**

#### **2.1.3.2.1 Key secondary efficacy endpoints**

The key secondary endpoints are:

- The percent change in calculated LDL-C from baseline to Week 24 in the mITT population, using all LDL-C values during the efficacy treatment period (on-treatment estimand);
- The percent change in calculated LDL-C from baseline to Week 12 (ITT estimand);
- The percent change in calculated LDL-C from baseline to Week 12 (on-treatment estimand);
- The percent change in Apo B from baseline to Week 24 (ITT estimand);
- The percent change in Apo B from baseline to Week 24 (on-treatment estimand);
- The percent change in non-HDL-C from baseline to Week 24 (ITT estimand);
- The percent change in non-HDL-C from baseline to Week 24 (on-treatment estimand);
- The percent change in TC from baseline to Week 24 (ITT estimand);
- The percent change in Apo B from baseline to Week 12 (ITT estimand);
- The percent change in non-HDL-C from baseline to Week 12 (ITT estimand);
- The percent change in TC from baseline to Week 12 (ITT estimand);
- The proportion of patients reaching calculated LDL-C <70 mg/dL (1.81 mmol/L) at Week 24 (ITT estimand);
- The proportion of patients reaching calculated LDL-C <70 mg/dL (1.81 mmol/L) at Week 24 (on-treatment estimand);
- The percent change in Lp(a) from baseline to Week 24 (ITT estimand);
- The percent change in HDL-C from baseline to Week 24 (ITT estimand);

- The percent change in fasting TG from baseline to Week 24 (ITT estimand);
- The percent change in Apo A-1 from baseline to Week 24 (ITT estimand);
- The percent change in Lp(a) from baseline to Week 12 (ITT estimand);
- The percent change in HDL-C from baseline to Week 12 (ITT estimand);
- The percent change in fasting TG from baseline to Week 12 (ITT estimand);
- The percent change in Apo A-1 from baseline to Week 12 (ITT estimand).

#### **2.1.3.2.2 Other secondary efficacy endpoints**

- The proportion of patients with calculated LDL-C <100 mg/dL (2.59 mmol/L) at Weeks 12 and Week 24 (ITT estimand);
- The proportion of patients reaching calculated LDL-C <70 mg/dL (1.81 mmol/L) at Week 12 (ITT estimand);
- The absolute change in calculated LDL-C (mg/dL and mmol/L) from baseline to Week 12 and Week 24 (ITT estimand);
- The absolute change in Apo B/Apo A-1 ratio from baseline to Week 12 and Week 24 (ITT estimand);
- The proportion of patients with Apo B <80 mg/dL (0.8 g/L) at Week 12 and Week 24 (ITT estimand);
- The proportion of patients with non-HDL-C <100 mg/dL (2.59 mmol/L) at Week 12 and Week 24 (ITT estimand);
- The proportion of patients with non-HDL-C <130 mg/dL (3.37 mmol/L) at Week 12 and Week 24 (ITT estimand);
- The proportion of patients with calculated LDL-C <70 mg/dL (1.81 mmol/L) and/or ≥50% reduction in calculated LDL-C (if calculated LDL-C ≥70 mg/dL [1.81 mmol/L]) at Week 12 and Week 24 (ITT estimand);
- The proportion of patients with ≥50% reduction in calculated LDL-C at Week 12 and Week 24 (ITT estimand);
- The absolute change in TC/HDL-C ratio from baseline to Week 12 and Week 24 (ITT estimand);
- The percent change in TC from baseline to Week 12 and 24 (on-treatment estimand);
- The percent change in Apo B from baseline to Week 12 (on-treatment estimand);
- The percent change in non-HDL-C from baseline to Week 12 (on-treatment estimand);
- The percent change in Lp(a) from baseline to Week 12 and 24 (on-treatment estimand); The proportion of patients reaching calculated LDL-C <100 mg/dL (2.59 mmol/L) at Week 24 (on-treatment estimand).

#### **2.1.4 Safety endpoints**

The safety analysis will be based on the reported adverse events (AEs) and other safety information, such as clinical laboratory data, electrocardiogram (ECG) and vital signs.

### ***Observation period***

The period of safety observation starts from the time when the patient gives informed consent and is divided into the following periods:

- The PRE-TREATMENT period: defined as the time from the signed informed consent up to the first dose of double-blind IMP;
- The treatment-emergent adverse event (TEAE) period: defined as the time from the first dose of double-blind IMP up to the day of last dose of double-blind IMP injection+70 days (10 weeks) as residual effect of alirocumab is possible until 10 weeks after the discontinuation of double-blind IMP injection.

The TEAE period will include:

- The TREATMENT period defined as the time from the first dose of double-blind IMP up to the day of last dose of double-blind IMP injection + 21 days, as serum concentration of alirocumab is expected to be  $>10 \mu\text{g/mL}$  for approximately 21 days following administration of 150 mg, and because throughout the previous studies it was observed that when alirocumab concentrations declined below this concentration, decrease in effect on LDL-C is observed.
- The RESIDUAL TREATMENT defined as the time from the day of last dose of double-blind IMP injection + 22 days up to the day of last dose of double-blind IMP injection + 70 days (10 weeks).
- The POST-TREATMENT period: defined as the time starting the day after the end of the TEAE period (ie, 71 days after the day of last dose of double-blind IMP injection).

The on-study observation period is defined as the time from the day of first dose of double-blind IMP (capsule or injection, whichever comes first) until the last protocol planned visit of the patient. The last protocol planned visit is defined as the follow-up visit if done, or else 32 weeks after the randomization of the patient.

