9.2 SAFETY ENDPOINTS

Observation period

The observation of safety data will be as follows:

- PRE-TREATMENT period: The PRE-TREATMENT observation period is defined from the signed informed consent up to the first dose of double-blind IMP (injection or capsule, whichever comes first).
- TEAE period: The TEAE observation period is defined as the time from the first dose of double-blind IMP (injection or capsule, whichever comes first) to the last dose of double-blind IMP injection + 70 days (10 weeks) as residual effect of treatment is expected until 10 weeks after the stop of double-blind IMP.
- POST-TREATMENT period: The POST-TREATMENT observation period is defined as the time starting the day after the end of the TEAE period up to the end of the study (see definition in [Section 6.2.1](#)).

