11.3.2 Safety population

The safety population considered for safety analyses will be the randomized patients who actually received at least 1 dose or part of a dose of the double-blind IMP (injection or capsule). Patients will be analyzed according to the treatment actually received (alirocumab or ezetimibe).

In addition:

- Randomized patients for whom it is unclear whether they took the study medication will be included in the safety population as randomized.
- For patients receiving study drug from more than 1 treatment group during the trial, the treatment group allocation for as-treated analysis will be the one in which the patient was treated with the longest duration.

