11.4.3 Analyses of safety data

The summary of safety results will be presented by treatment group. No formal inferential testing will be performed. Summaries will be descriptive in nature.

All safety analyses will be performed on the Safety population using the following common rules:

- The baseline value is defined generally as the last available value before double IMP (injection or capsule, whichever comes first).

The following definitions will be applied to laboratory parameters and vital signs.

- The potentially clinically significant abnormality (PCSA) values are defined as abnormal values considered medically important by the Sponsor according to predefined criteria/thresholds based on literature review and defined by the Sponsor for clinical laboratory tests and vital signs.
- PCSA criteria will determine which patients had at least 1 PCSA during the TEAE period, taking into account all evaluations performed during the TEAE period, including unscheduled or repeated evaluations. The number of all such patients will be the numerator for the on-treatment PCSA percentage.

- Treatment period: the treatment period used for quantitative analysis is defined as the time from first dose of double-blind IMP (injection or capsule, whichever comes first) to the last dose of double-blind IMP injection + 21 days.

AE definition:

- Pre-treatment AEs are AEs that developed or worsened or became serious during the PRETREATMENT period;
- Treatment-emergent AEs (TEAEs) are AEs that developed or worsened or became serious during the TEAE period;
- Post-treatment AEs are AEs that developed or worsened or became serious during the POSTTREATMENT period.

Drug induced liver injury

The liver function tests, namely ALT, AST, alkaline phosphatase and total bilirubin, are used to assess possible drug induced liver toxicity. The proportion of patients with PCSA values at any post-baseline visit by baseline status will be displayed by treatment group for each parameter. A graph of distribution of peak values of ALT versus peak values of total bilirubin will also be presented. Note that the ALT and total bilirubin values are presented on a logarithmic scale. The graph will be divided into 4 quadrants with a vertical line corresponding to $3 \times \text{ULN}$ for ALT and a horizontal line corresponding to $2 \times \text{ULN}$ for total bilirubin.

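### The TEAE and TREATMENT periods end by the last injection alone, so late on-drug data from ezetimibe patients who stop injections but continue capsules can fall outside them

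*SAP*

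**What the plan says.** In SAP 2.1.4 (Observation period) the TEAE period is "defined as the time from the first dose of double-blind IMP up to the day of last dose of double-blind IMP injection+70 days", on the ground that alirocumab may still have a residual effect for 10 weeks after injections stop. The TREATMENT period inside it runs "up to the day of last dose of double-blind IMP injection + 21 days", a length justified by how long alirocumab serum concentrations stay high enough to act on LDL-C. The post-treatment period starts "71 days after the day of last dose of double-blind IMP injection".

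The protocol agrees. Section 9.2 starts the TEAE period at the first injection or capsule and ends it at the "last dose of double-blind IMP injection + 70 days (10 weeks) as residual effect of treatment is expected until 10 weeks" after stopping. Section 11.4.3 says "the treatment period used for quantitative analysis is defined as the time from first dose of double-blind IMP", again injection or capsule, and closes that period 21 days after the last injection.

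The safety population is wider than the injection: Protocol 11.3.2 admits "randomized patients who actually received at least 1 dose or part of a dose of the double-blind IMP (injection or capsule", and SAP 2.3.2 does the same.

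In the ezetimibe arm the injections are placebo and are planned to end at Week 22. Ezetimibe itself is a daily capsule (Protocol 8.5), taken up to the day before the end-of-treatment visit (Protocol 8.1.2).

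Elsewhere the plan keeps the two stop dates apart:
- The efficacy treatment period ends at the earlier of last injection + 21 days and last capsule + 3 days (Protocol 11.3.1.2, SAP 2.3.1.2).
- Injection and capsule exposure are computed separately (Protocol 11.4.1.1, SAP 2.4.3.1).
- An interruption may concern injections or capsules (Protocol 10.3.1).
- The contraception period is counted from whichever component was taken last (Protocol 7.2.3 and 8.9.2).

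**The concern.** Either component can open the safety periods, but only the injection closes them. That suits the alirocumab arm, where the injection is the drug. In the ezetimibe arm the closing date is set by a placebo. If such a patient stops injecting and goes on taking capsules, the TEAE period can close while the patient is still on active drug.

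Adverse events after that point move to the post-treatment tables of SAP 2.4.5.1. Those tables cover all post-treatment AEs and SAEs, so most such events remain visible. Some TEAE-based outputs have no post-treatment counterpart in the SAP:
- AEs leading to treatment discontinuation are tabulated for the treatment-emergent and pre-treatment periods only.
- Adjudicated CV events are summarised only if treatment-emergent.
- PCSAs are counted only within the TEAE period.
- Kaplan-Meier curves for AEs are censored at its end.

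The shorter TREATMENT period does not classify AEs. It governs the last and worst on-treatment laboratory and vital-sign values (SAP 2.4.5), HbA1c (SAP 2.4.6) and the low LDL-C endpoint (SAP 2.1.5).

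Safety documentation is one of the two stated reasons for enrolling 600 patients when 96 suffice for the efficacy test (Protocol 11.1), so the comparator's safety windows should be right.

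**Working it through.** **Inputs.** Day 1 is Week 0, so Week w falls on Day 1 + 7w. The last planned injection is Week 22 (Day 155). The last capsule is the day before the Week 24 visit (Day 169), that is Day 168. The ezetimibe arm has 200 patients.

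**The plan's own figure.** Protocol section 4 equates 8 weeks of follow-up with 10 weeks after the last dose. Day 155 + 70 = Day 225, which is the Week 32 visit in the flow chart. It reproduces exactly.

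**Formulas.** Let L be the day of the last injection and suppose capsules continue to Day 168.
- Capsule days after the TEAE period = max(0, 168 − (L + 70)).
- Capsule days after the TREATMENT period = max(0, 168 − (L + 21)).

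| Last injection | TREATMENT end | Capsule days after it | TEAE end | Capsule days after it (share of 168) |
|---|---|---|---|---|
| Week 0, Day 1 | Day 22 | 146 | Day 71 | 97 (58%) |
| Week 2, Day 15 | Day 36 | 132 | Day 85 | 83 (49%) |
| Week 4, Day 29 | Day 50 | 118 | Day 99 | 69 (41%) |
| Week 8, Day 57 | Day 78 | 90 | Day 127 | 41 (24%) |
| Week 12, Day 85 | Day 106 | 62 | Day 155 | 13 (8%) |
| Week 14, Day 99 | Day 120 | 48 | Day 169 | 0 |
| Week 20, Day 141 | Day 162 | 6 | Day 211 | 0 |
| Week 22, Day 155 | Day 176 | 0 | Day 225 | 0 |

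**Cut-off for AEs.** L + 70 < 168 requires L ≤ Day 97. With the ±3-day windows, a Week 14 injection on Day 96 and a last capsule on Day 171 leave 171 − 166 = 5 days outside, which is the most that can arise from Week 14 on.

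**Scheduled samples.** During treatment HbA1c is drawn only at Weeks 12 and 24. The Week 24 sample (Day 169) is outside the TREATMENT period if the last injection is at Week 20 or earlier (141 + 21 = 162). The Week 12 sample (Day 85) is outside if the last injection is at Week 8 or earlier (57 + 21 = 78).

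**Size across the arm.** The documents give no rate of stopping injections while continuing capsules. Assume 0.5% to 5% of 200 patients, that is 1 to 10. Planned capsule days are 200 × 168 = 33,600.
- Low end: 1 × 13 = 13 days, 0.04%.
- High end: 10 × 97 = 970 days, 2.9%.

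**The case against.** The strongest reply is that the protocol hardly foresees this patient. Permanent discontinuation is defined for the IMP as a whole (10.3.2). Discontinued patients continue visits without study treatment and have an end-of-treatment assessment within 5 days if possible (10.3.4), and capsules run only to the day before that visit, early or not (8.1.2). The two stop dates differ by design even in completers, so recording both does not show that long capsule-only treatment was expected. An interruption followed by resumed injections does not move the last-injection date. All of this stands as a limit on frequency. Even so, no section says that capsules must stop when injections do, and interruption of one component alone is allowed.

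It is also fair that safety is descriptive, that AEs are recorded to the follow-up visit, and that on-study deaths do not depend on the TEAE end. That softens the consequence but does not restore the outputs that lack a post-treatment counterpart.

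A capsule-only patient, with no last injection at all, is close to theoretical because both first doses are given at the site (Protocol 10.1.2.1). SAP 2.5.3 imputes a missing last-injection date but does not say whether this covers an injection never given. That needs a clarifying line and no more.

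A further objection concerns the remedy. Extending the TREATMENT period by the capsule date in both arms would label placebo-capsule time as alirocumab treatment. With a last injection on Day 29 and capsules to Day 168, it would run to Day 171 instead of Day 50, against the 21-day rationale in SAP 2.1.4. This objection is right, and the fix below leaves that period alone.

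**Conclusion.** The gap is real but conditional. An on-drug AE leaves the TEAE tables only if an ezetimibe patient has the last injection by about Week 12, continues capsules, and has the event more than 70 days after that injection. For laboratory and HbA1c values the reach is wider, to a last injection at Week 20, because the TREATMENT period is shorter. Completers and patients who stop both components together lose nothing.

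Three stronger readings are tempting but unsupported:
- A reader might infer that any ezetimibe patient who stops injections early has on-drug AEs moved to post-treatment. The arithmetic gives none from Week 14 on nominal days, and none at any time if capsules stop too.
- A reader might take the shares of 8% to 58% as trial-level effects. They describe single hypothetical patients. Across the arm the range is 0.04% to 2.9% of planned capsule days, and that rests wholly on the assumed 0.5% to 5%.
- A reader might infer that the rule flatters alirocumab. It under-counts ezetimibe events, so any distortion makes alirocumab look worse by comparison.

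**What to change.** In both arms, end the TEAE period at the later of last injection + 70 days and last capsule + a stated interval. The 3 days of the efficacy treatment period is a candidate, but it was set for efficacy and needs its own safety justification. For any never-injected patient, use the capsule date. Extend the rule for a missing last-capsule date in SAP 2.5.3, which now serves only the efficacy period, to the safety period.

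Keep the injection-based TREATMENT period as the main definition. Add a supplementary ezetimibe-arm summary of on-treatment laboratory and HbA1c values that counts time up to the last capsule + the same interval.

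With 3 days and capsules to Day 168 (168 + 3 = 171), the TEAE end moves from Day 71 to Day 171 for a last injection at Week 0, from Day 155 to Day 171 at Week 12, and from Day 169 to Day 171 at Week 14. It stays at Day 225 for completers.

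The cost is a changed derivation, one extra summary, and aligned wording in the protocol synopsis, Protocol 9.2 and 11.4.3, and SAP 2.1.4. The medication windows in SAP 2.1.2 also hang on last injection + 70 days and must follow. The change should be recorded in SAP 1.5, which now reports no major departures from the protocol.

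The downside is that an alirocumab patient who stops injections but continues placebo capsules gets the same longer TEAE window, up to 100 days in the extreme case (171 − 71). That is the price of one rule for both arms.
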